9.5.2.2 Time to First Platelet Response (2)

A 2-sided log-rank test stratified by tumor type and baseline platelet count will be performed to determine whether time to first platelet response is significantly different between treatment groups. The hazard ratio of achieving platelet response for romiplostim vs placebo and its corresponding 2-sided 95% CI will be provided using a stratified Cox regression model.

Kaplan-Meier curves for the time to achieving first platelet response will be presented along with Kaplan-Meier rates and 2-sided 95% CIs at specified time points (week 3, week 4, etc) for each treatment group. In addition, Kaplan-Meier quartiles (median, 25th, and 75th percentiles) will be estimated with 2-sided 95% CI, if estimable.

9.5.2.3 Duration-adjusted Event Rate of \geq Grade 2 Bleeding Events (3)

Duration-adjusted event rate of grade \geq 2 bleeding events will be calculated as described in [Section 5](#). The number of grade \geq 2 bleeding events will be summarized for each treatment group. An Andersen-Gill model ([Andersen and Gill, 1982](#)) with a robust variance estimator ([Lin and Wei, 1989](#)), stratified by tumor type and baseline platelet count, will be used to analyze recurrent bleeding events and will provide hazard ratio with 95% CI and p-value comparing treatment groups (see [Appendix A. Code Fragment for Andersen-Gill Model](#) for sample SAS code).

9.5.2.4 Overall Survival (4)

[figure not shown]
A 2-sided log rank test stratified by tumor type will test differences of survival rates between the two treatment groups. A hazard ratio with 95% CI from a stratified Cox regression model will describe the treatment effect. The cause of death will be summarized for each treatment group.

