## 7.2 Method of Treatment Assignment

Subjects will be randomized in 2:1 allocation ratio, to romiplostim or placebo, respectively, in double-blind manner.

The randomization number will be provided by the IVRS/IXRS system.

The randomization will be stratified by tumor type and baseline platelet count ( $< 50 \times 10^9/L$ ,  $\geq 50 \times 10^9/L$ ). Gastrointestinal tract cancers, including tumors of the esophagus or stomach, will be included in one stratum, pancreatic cancers will be included in a second stratum, and colorectal cancers, including tumors of the colon or rectum, will be included in a third stratum.

The randomization date is to be documented in the subject's medical record and on the enrollment CRF.

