#### **10.3.2.2.2.4 Overall Survival**

Overall survival time is calculated from study day 1 to death. Subjects who have not died will be censored at their last contact date. A 2-sided stratified log rank will test

---

differences of survival rates between the two treatment groups. A hazard ratio with 95% CI from a stratified Cox regression model will describe the treatment effect.

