Once eligibility is confirmed, subjects will be randomized on day 1 of the study in a 2 to 1 ratio to receive either romiplostim or placebo, respectively. Randomization will be stratified by tumor type and by baseline platelet count ($< 50 \times 10^9/L$, $\geq 50 \times 10^9/L$). Baseline platelet count is defined as last platelet count measured prior to the time of the planned investigational product administration. Gastrointestinal cancers, including tumors of the esophagus or stomach, will be included in one stratum, **pancreatic cancers in a second stratum, and colorectal cancers, including adenocarcinomas of the colon or rectum, will be included in a third stratum**. Subjects will then enter the treatment period, during which time they will return to the clinic weekly for local platelet counts, undergo dose titrations as needed, and investigational product administration. If there are multiple platelet values performed on a study visit date, the platelet value from the test performed most immediately prior to the time of the planned investigational product and/or non-investigational product administration will be recorded as the platelet value for that study visit date and will be used to determine the subject's dose of investigational product and, when applicable, chemotherapy dose modifications which include dose reductions, delays, omissions, and discontinuations. Subjects will receive weekly subcutaneous injections of investigational product throughout the treatment period, starting at 2 $\mu g/kg$ and increasing by

increments of 1 μ g/kg to a maximum dose of 10 μ g/kg to reach a target platelet count of $\geq 100 \times 10^9/L$. **Dose adjustment rules will be followed according to protocol Table 7-1. If the subject will be receiving concomitant chemotherapy on a study visit date, investigational product will be administered immediately after the completion of chemotherapy infusion on chemotherapy day 1. If continuous infusion 5 fluorouracil (5-FU) over 46-48 hours is part of the chemotherapy regimen the investigational product may be administered prior to beginning or during the continuous infusion 5-FU.**

Subjects will have a follow-up visit 1 week after the last dose of investigational product.

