9.7.1 Analyses of Pharmacokinetic or Pharmacokinetic/Pharmacodynamic Endpoints

The Clinical Data Interchange Standards Consortium (CDISC) Analysis Data Model (ADaM) standard will be adopted to create the Analysis Dataset for Pharmacokinetics Concentrations (ADPC). The ADPC dataset includes the following variables: 1) subject level information (eg., subject ID, country, planned treatment, actual treatment received, population flags); 2) PK variables (eg., concentration, actual and scheduled PK sampling time); 3) Dosing variables (eg., planned and actual dose(s), start time, stop time and duration of drug infusion, time relative to first infusion start); 4) Physical measurement variables (eg., demographics, selected baseline characteristics and laboratory measurements) and 5) Miscellaneous variables (eg., study specific variables). The pharmacokinetic analysis will be carried out for PK analysis set.

10. Changes From Protocol-specified Analyses

There are no changes to the protocol-specified analyses.

11. Literature Citations / References

Collett D. Modeling Survival Data In Medical Research, Second Edition. Chapman and Hall, Boca Raton. 2003

Shapiro, S. S., and Wilk, M. B. (1965), An analysis of variance test for normality (complete samples), *Biometrika* 52, 591–611.

Van Elteren PH. "On the Combination of Independent Two-Sample Tests of Wilcoxon." *Bulletin of the International Statistical Institute* 1960;37:351–361.

12. Data Not Covered by This Plan

Further analyses of pharmacokinetic or Pharmacokinetic/Pharmacodynamic endpoints, [REDACTED]

[REDACTED]

[REDACTED]

13. Appendices

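### The SAP's overall-survival test omits the baseline platelet stratum and leaves the Cox strata unnamed, unlike the randomization and every other formally tested efficacy endpoint

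*SAP*

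**What the plan says.** Both documents stratify randomization by two factors. SAP 3.1 says "Randomization will be stratified by tumor type and by baseline platelet count", and Protocol 7.2 says "The randomization will be stratified by tumor type and baseline platelet count". With three tumor groups and two platelet groups, this gives six cells.

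For OS, SAP 9.5.2.4 says "A 2-sided log rank test stratified by tumor type will test differences of survival rates between the two treatment groups", followed by "A hazard ratio with 95% CI from a stratified Cox regression model will describe the treatment effect". The Cox factors are not stated. Protocol 10.3.2.2.2.4 is more general: "A 2-sided stratified log rank will test" for a difference in survival, again with no factors named.

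For the other time-to-event endpoints the SAP is explicit. Time to first platelet response (9.5.2.2): "A 2-sided log-rank test stratified by tumor type and baseline platelet count will be performed". Bleeding (9.5.2.3): an Andersen-Gill model "stratified by tumor type and baseline platelet count, will be used to analyze recurrent bleeding events".

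SAP 9.1 places OS fourth among the secondary endpoints in the fixed sequence at two-sided 0.05. SAP section 10 states "There are no changes to the protocol-specified analyses".

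**The concern.** OS is formally tested and acts as a gate. Platelet transfusion and platelet response by week 4 come after it in the sequence and can be tested only if OS is significant. Its analysis would be expected to follow the factors used to allocate treatment, as the rest of the SAP does. Leaving one out without explanation raises two issues.

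- If baseline platelet count predicts survival, a log-rank test that ignores it overstates the variance of the treatment comparison. It then becomes conservative and loses some power.
- The strata behind the OS hazard ratio are not defined. A reader cannot tell whether the Cox model follows the log-rank test (tumor type only) or the randomization (both factors).

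Timing matters. Under SAP 7.2 the study is unblinded at the primary analysis, while SAP 7.3 leaves OS to the final analysis. A correction made between the two would be open to the suspicion that it was driven by the data.

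**Working it through.** **Step 1: the texts side by side.**

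| Where | Comparison | Factors |
|---|---|---|
| SAP 3.1, Protocol 7.2 | Randomization | tumor type, platelet count |
| SAP 9.5.1 | Primary endpoint, CMH | both |
| SAP 9.5.2.1 | Nadir, linear regression | both, as model terms |
| SAP 9.5.2.2 | Time to platelet response, log-rank | both |
| SAP 9.5.2.3, Appendix A | Bleeding, Andersen-Gill | both |
| SAP 9.5.2.4 | OS, log-rank | **tumor type only** |
| SAP 9.5.2.4 | OS, Cox | **not named** |
| SAP 9.5.2.5 | Transfusion, CMH | both |
| SAP 9.5.2.6 | Platelet response by week 4, CMH | both |
| Protocol 10.3.2.2.2.4 | OS, log-rank and Cox | not named |

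OS is the only formally tested efficacy endpoint that leaves the platelet factor out.

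**Step 2: is there a plan figure to reproduce?** No. The documents give no hazard ratio (HR), number of deaths or power for OS. They also give no proportion of subjects below 50 × 10^9/L and no prognostic effect of platelet count on survival. Everything below rests on assumptions beyond the documented sample size of 162 and the 2:1 allocation.

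**Step 3: scale of OS power.** By the Schoenfeld formula, power = Φ(√(d·p·(1−p))·|ln HR| − 1.96), with p = 2/3. With d = 100 deaths (assumed), √(100 × 2/9) = 4.714.

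- HR 0.6: 4.714 × 0.511 − 1.96 = 0.45, power 67%
- HR 0.7: 4.714 × 0.357 − 1.96 = −0.28, power 39%
- HR 0.8: 4.714 × 0.223 − 1.96 = −0.91, power 18%

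**Step 4: effect of restoring the factor.** Three sets of simulated trials (162 subjects, stratified 2:1 allocation) compared a log-rank test on three tumor strata with one on six tumor-by-platelet strata.

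- Set A: 4,000 runs per scenario, blocks of 3, tumor mix 20/20/60%, reference median OS 20 months, 92–123 deaths, treatment HR 0.6.
- Set B: 3,000 runs, 65–85% deaths, 25% low platelets, treatment HR 0.70.
- Set C: 3,000 runs, tumor mix 20/20/60%, treatment HR 0.70. The rows below have about 95–108 deaths unless marked.

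| Prognostic HR, <50 vs ≥50 | Set (share <50) | Power, tumor only | Power, both | Change (points) |
|---|---|---|---|---|
| 1 | A (15%) | 66.4% | 65.1% | −1.3 |
| 1 | A (30%) | 65.6% | 64.1% | −1.5 |
| 1 | B (25%) | 43.8% | 43.1% | −0.7 |
| 1.5 | A (15%) | 66.4% | 65.4% | −1.0 |
| 1.5 | A (30%) | 68.1% | 68.2% | +0.1 |
| 1.5 | C (10%) | 40.2% | 39.0% | −1.2 |
| 1.5 | C (25%) | 39.8% | 39.0% | −0.8 |
| 2 | A (15%) | 65.9% | 66.0% | +0.1 |
| 2 | A (30%) | 67.5% | 69.2% | +1.7 |
| 2 | B (25%) | 43.5% | 45.3% | +1.8 |
| 2 | C (10%) | 39.5% | 39.9% | +0.4 |
| 2 | C (25%) | 39.7% | 41.6% | +1.9 |
| 3 | A (15%) | 63.7% | 67.7% | +4.0 |
| 3 | A (30%) | 62.5% | 69.5% | +7.0 |
| 3 | B (25%) | 37% | 44% | +7 |
| 3 | C (25%) | 34.8% | 40.4% | +5.6 |
| 3 | C (25%, about 64 deaths) | 23.3% | 27.7% | +4.4 |

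In set C with about 51–59 deaths and prognostic HR 1 to 2, the two tests differed by no more than 0.5 point.

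**Step 5: type I error at nominal 5%.** In set A the tumor-only test gave 3.8–5.7% and the two-factor test 4.6–5.9%. The Monte Carlo standard error is √(0.05 × 0.95/4000) = 0.34 points. The lowest tumor-only value (3.8%) is at prognostic HR 3. In set B at prognostic HR 3 the rates were 3.6% and 4.4%. The 5.9% comes from the same set A setting as the +7.0 power change, so part of that gain may be simulation noise.

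**The case against.** The case against giving this weight is substantial, and most of it stands.

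- **Conflict with the protocol.** A reader might infer that the SAP contradicts the protocol and that the statement in SAP section 10 is therefore false. The documents do not support that. Protocol 10.3.2.2.2.4 asks for a stratified test without naming factors, and a test stratified by tumor type is a stratified test. Both randomization factors are the natural reading, but that is an inference.
- **Two p-values.** A reader might also infer that the plan leaves two OS p-values open. It does not: the SAP names one log-rank test. What is open is the Cox strata, and the text does not say that the Cox model takes over the log-rank factor.
- **Validity.** Omitting a randomization factor does not create false positives. The possible loss is efficiency.
- **Size.** A gain above about 2 points needs a prognostic HR near 3. Everyone enrolled must have a count of at most 85 × 10^9/L on day 1 (Protocol 6.1), so the contrast is below 50 against 50 to 85. Nothing in the documents supports a threefold hazard across that range.
- **Leverage.** OS is reached only after the primary endpoint, nadir, time to response and bleeding all succeed. The sample size is justified for the primary endpoint only.
- **Sparse cells.** In set C the smallest of the six cells averaged about 2 subjects with 10% low platelets and 6–7 with 25%. This is a fair caution, but the loss stayed at about 1.5 points or less in every scenario, so it is not a strong reason to drop the factor.

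**Conclusion.** The inconsistency is real and can be read directly from the text. SAP 9.5.2.4 uses one of the two randomization factors for the OS log-rank test and names none for the Cox model. Every other formally tested efficacy analysis accounts for both. The documents give no reason and do not show whether the omission was deliberate.

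The consequence is modest. The OS test is valid and at most somewhat conservative. Restoring the platelet factor changes power by roughly −1.5 to +2 points at a prognostic HR of 1 to 2, and by about +4 to +7 points only near 3. These ranges depend on assumed tumor mix, share of low-platelet subjects, number of deaths and treatment effect. A large loss of power cannot be claimed from the documents.

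The change is still worth making. It aligns a gatekeeping endpoint with the randomization, defines the hazard ratio, removes possible conservatism and costs little if platelet count turns out not to be prognostic.

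**What to change.** Replace the test and model statements in SAP 9.5.2.4 with:

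*A 2-sided log-rank test stratified by tumor type and baseline platelet count (<50, ≥50 × 10^9/L); hazard ratio and 95% CI from a Cox model stratified by the same two factors.*

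Make the change before unblinding at the primary analysis. If tumor type alone was intended, the SAP should instead give the reason, name the Cox factors and record the choice in section 10. Either way the cost is a sentence or two in the SAP, with no new data and no change to trial conduct.

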9.5.2.5 Platelet Transfusion(s) During the Treatment Period (5)

The proportion of subjects with at least 1 platelet transfusion during the treatment period will be provided with a 95% CI for each treatment group and the difference in proportions between treatment groups will be provided with a 95% CI. A 2-sided CMH test will be used to compare groups controlling for the stratification factors of tumor type and baseline platelet count. The Mantel-Haenszel estimate of common odds ratio for romiplostim vs placebo will be estimated along with a 95% CI.

9.5.2.6 Achieving a Platelet Count $\geq 100 \times 10^9/L$ at any Time After Study Day 1 to Week 4 (6)

The proportion of subjects achieving platelet count $\geq 100 \times 10^9/L$ at any time after study day 1 to week 4 (ie, 7 days after the third planned dose of investigational product) in the absence of platelet transfusions during the preceding 7 days, will be provided with a 95% CI for each treatment group and the difference in proportions between treatment groups will be provided with a 95% CI. A 2-sided CMH test will be used to compare groups controlling for the stratification factors of tumor type and baseline platelet count. The Mantel-Haenszel estimate of common odds ratio for romiplostim vs placebo will be estimated along with a 95% CI.

**9.6 Safety Analyses****9.6.1 Analyses of Primary Safety Endpoint(s)**

The Medical Dictionary for Regulatory Activities (MedDRA) version 25.1 or later will be used to code adverse events. The adverse events will be summarized by treatment group using the safety analysis set.

The subject incidence will be summarized for all **TEAEs**, serious **TEAEs**, **TEAEs** leading to withdrawal of investigational product, **TEAEs** leading to withdrawal of chemotherapy agent,

treatment-related TEAEs, serious treatment-related TEAEs, grade ≥ 3 TEAEs, and fatal TEAEs by system organ class and preferred term.

In addition, subject incidence and duration-adjusted rates for events of interest will be summarized. Subject listing of all adverse events occurred from the first dose of IP to 30(+5) days after last dose of the IP or last dose of on-study chemotherapy (up to 3 cycles), whichever occurs later, will be provided. A separate listing will be provided for all the AEs (including AEs starting in LTFU period).

An Independent Biostatistics Group (IBG) will perform periodic safety analyses for review by an independent DMC. DMC will review all available safety data on a regular basis during the study and will make recommendations concerning the continuation or alteration of the study based on its data review. More details are included in the DMC charter.

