### 3.2.4.3 Ongoing Investigator-sponsored Study

In a randomized, controlled study with a cross-over design, subjects with CIT (platelets  $< 100 \times 10^9/\text{L}$ ) for at least 4 weeks despite chemotherapy delay or dose

reduction were randomized 2:1 romiplostim (2  $\mu$ g/kg) to control (observation) (Soff et al, 2017).

The primary endpoint was the proportion of patients achieving a platelet count  $> 100 \times 10^9/L$  by the end of a 3-week treatment period. Secondary endpoints included ability to tolerate resumption of chemotherapy for at least 2 cycles without recurrence of CIT.

An interim analysis was conducted with 23 subjects (n = 15 romiplostim arm, 8 observation arm). Platelet counts for 14 subjects (93%) in the romiplostim arm corrected within 3 weeks. In the observation arm, the platelet levels in 1 subject (12.5%) spontaneously corrected in 3 weeks, representing a statistically significant difference ( $p = 0.001$ ). The observational arm was discontinued and all subsequent subjects were enrolled in the treatment arm.

Of the 32 subjects who received up front romiplostim, 27 subjects (84%) were able to achieve platelet counts  $\geq 100 \times 10^9/L$  by the third week, and 25 subjects (78%) in the romiplostim group were able to resume chemotherapy after correction of their CIT.

There was no evidence of bone marrow side effects from romiplostim treatment. Four (12.5%) of 32 subjects experienced a thromboembolic event (Soff et al, 2017).

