## 5. Study Design

### 5.1 Overall Design

This is a phase 3, randomized, placebo-controlled, multicenter, international study for the treatment of CIT in adult subjects receiving oxaliplatin-based chemotherapy for the treatment of gastrointestinal, pancreatic, or colorectal cancer. Subjects must have a platelet count  $\leq 85 \times 10^9/L$  on day 1 of the study. The study will consist of a screening period of up to 4 weeks, a treatment period long enough to allow for assessment of 3 planned cycles of chemotherapy, a follow-up visit, and long-term follow-up (LTFU). Given that subjects will be assessed for 3 planned cycles of chemotherapy, the oxaliplatin-based chemotherapy cycles are 2-3 weeks in duration, and the investigational product dose adjustment guidelines allow for up to 12 weeks of dosing before a subject is declared a non-responder, the majority of study subjects will receive investigational product for a range of between **7-21 weeks**.

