#### **7.4.1.2 Non-Amgen Non-investigational Product: Standard-of-care Chemotherapy**

The following will be specified prior to the first administration of investigational product: chemotherapy agents in the planned treatment regimen, planned total dose and unit of each agent, number of days per cycle, and planned dosing schedule. The planned chemotherapy regimen reflects what the investigator considers standard dose and schedule for that regimen. The following will be captured during the treatment period: the actual chemotherapy dose and unit administered; date of administration; whether the subject experienced a dose reduction, delay, or omission due to thrombocytopenia; whether the subject experienced chemotherapy treatment discontinuation due to thrombocytopenia; and whether there was a reason other than thrombocytopenia for dose reduction, delay, omission, or discontinuation. An independent adjudicator will periodically verify the reason for chemotherapy dose modification in the study.

Chemotherapy dose modifications include dose reductions, dose delays, dose omissions, and treatment discontinuations. During the 3 on study cycles, a chemotherapy delay must be increments of 1 week to align with the weekly study visits if applicable.

Following enrollment and initiation of investigational product, the first cycle of chemotherapy during the treatment period should not be administered until platelet counts are  $\ge 100 \times 10^9/L$  or until **at least** week 4, whichever occurs first. **If platelet counts at the start of chemotherapy cycle 1 are  $< 100 \times 10^9/L$ , recheck platelet count 1 week later and continue to hold until platelet count  $\ge 100 \times 10^9/L$ . Starting from week 4, subjects may start the first cycle of chemotherapy with dose**

adjustments according to the dose modification guidelines listed below. If the platelets remain  $< 100 \times 10^9/L$ , the investigator has the discretion to continue IP for dose escalation up to 12 weeks before beginning the first on-study chemotherapy cycle. After 12 weeks without starting study cycle 1 on IP, the subject is considered a non-responder.

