#### **10.3.2.3 Safety Analyses**

##### **10.3.2.3.1 Adverse Events**

The subject incidence of treatment-emergent adverse events will be summarized by system organ class, by preferred term according to Medical Dictionary for Regulatory Activities (MedDRA) for each treatment group. This summary for treatment-emergent adverse events will include the following categories:

- all adverse events
- fatal adverse events
- serious adverse events
- treatment-related adverse events
- adverse events of interest, such as hemorrhage and thrombotic/thromboembolic events
- adverse events leading to investigational product discontinuation

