Events categorized as AEs starting on or after first dose of investigational product as determined by “Did event start before first dose of investigational product” equal to “No” or missing on the Events eCRF; and up to and including 30 days after the last dose of investigational product (excluding events reported after End of Study date).

Any event which has started 30 days after the last dose of IP (i.e., during LTFU period) will not be considered as TEAE.

[figure not shown]
6. Analysis Sets

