8.4 Detection of Bias

Placebo subjects might drop out earlier than romiplostim subjects and we would detect this in our summary of disposition and IP exposure tables. Sensitivity analyses for the primary analysis specified in [Section 9.5.1](#) address the potential of early drop out or discontinuation.

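### The general TEAE tables give crude subject incidence only, over a window whose length depends on platelet response and so may differ by arm

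*SAP*

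**What the plan says.** **Measure.** SAP 9.6.1 opens its adverse event summaries with "The subject incidence will be summarized for all" TEAEs. It goes on to serious, grade ≥ 3, fatal and treatment-related TEAEs (including serious treatment-related ones) and those leading to withdrawal of IP or of a chemotherapy agent, by system organ class and preferred term. Protocol 10.3.2.3.1 likewise states: "The subject incidence of treatment-emergent adverse events will be summarized by system organ class". The only exposure-adjusted summary in SAP 9.6.1 is the next one: "subject incidence and duration-adjusted rates for events of interest will be summarized". The SAP does not list the events of interest; Protocol 10.3.2.3.1 gives hemorrhage and thrombotic/thromboembolic events as examples.

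**Window.** SAP Section 5 counts an event as treatment-emergent if it starts on or after the first IP dose and "up to and including 30 days after the last dose of investigational product".

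**What sets IP duration.** Protocol 5.1 says "the majority of study subjects will receive investigational product for a range of between" 7 and 21 weeks. Under Protocol 7.4.1.2, cycle 1 waits for a platelet count of 100 × 10⁹/L, or at least until week 4. If counts stay low, "the investigator has the discretion to continue IP for dose escalation up to 12 weeks before beginning the first on-study chemotherapy cycle". Later delays come in one-week steps. Protocol 7.4.1.1 stops IP after four consecutive weeks below 100 × 10⁹/L at the maximum dose.

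**What the SAP anticipates.** SAP 8.4 says "Placebo subjects might drop out earlier than romiplostim subjects" and relies on the disposition and exposure tables to show it. The sensitivity analyses it cites are for the primary efficacy analysis.

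**The concern.** Crude incidence rises with time observed. Here the observation window is not fixed by design. Its length follows from platelet response after randomization, which is what romiplostim is meant to change. If one arm is observed for longer on average, equal risk per week produces unequal percentages, and a real difference can be diluted or exaggerated.

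Overall safety of romiplostim is a stated objective, and the general TEAE tables are its broadest between-arm evidence. SAP Section 5 already defines a duration-adjusted adverse event rate over essentially the same window, but SAP 9.6.1 applies it only to events of interest. Serious, fatal and grade ≥ 3 events as categories are not among the examples named.

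**Working it through.** **1. Reproduce the plan's range.** IP weeks = (study week of cycle 1 start − 1) + 3 × cycle length.
- Shortest: start at week 2 with 2-week cycles, 1 + 6 = 7 weeks.
- Longest: 12 weeks of IP before cycle 1, then 3-week cycles, 12 + 9 = 21 weeks.

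Both agree with Protocol 5.1. Adding 30 days (30/7 = 4.3 weeks) gives TEAE windows of 11.3 and 25.3 weeks, a ratio of 2.24.

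**2. Inputs for an illustration by arm.** No document gives IP duration by arm, so these are assumptions built on the documents' figures.
- *Romiplostim response:* Protocol 3.2.4.2 reports, from one retrospective review, 59% responding one week after a single dose and 76% after two to three doses. I take 59% starting at week 2 and a further 8.5% at week 3 (the midpoint of 59% and 76% is 67.5%). The other 32.5% are the later starters.
- *Placebo response:* Protocol 3.2.4.3 reports "In the observation arm, the platelet levels in 1 subject (12.5%) spontaneously corrected in 3 weeks". I take 12.5% starting at week 3 and 87.5% later.
- *Delays:* one week per primary-endpoint failure. The design formula p² + ρp(1 − p) with ρ = 0.7 gives success of 0.09 + 0.147 = 0.237 on placebo and 0.36 + 0.168 = 0.528 on romiplostim. Mean delays are therefore 0.763 and 0.472 weeks.
- *Later starters:* they begin at the same week in both arms.

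**3. Mean window** = (mean start week − 1) + 6 + mean delay + 30/7, for 2-week cycles. At week 4 the mean start on romiplostim is 0.59 × 2 + 0.085 × 3 + 0.325 × 4 = 2.735, and on placebo 0.125 × 3 + 0.875 × 4 = 3.875.

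| Later starters begin at | Romiplostim window (weeks) | Placebo window (weeks) | Placebo time beyond the shorter window |
|---|---|---|---|
| Week 4 | 1.735 + 6 + 0.472 + 4.286 = 12.5 | 2.875 + 6 + 0.763 + 4.286 = 13.9 | 10% |
| Week 6 | 2.385 + 10.758 = 13.1 | 4.625 + 11.049 = 15.7 | 16% |
| Week 8 | 3.035 + 10.758 = 13.8 | 6.375 + 11.049 = 17.4 | 21% |

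With 3-week cycles every window is 3 weeks longer, and the shares are 9%, 14% and 18%.

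**4. Effect on a reported percentage.** Assume a constant and equal hazard, and 20% incidence on romiplostim. Placebo incidence is 1 − 0.8^(placebo window / romiplostim window): 22.0%, 23.4% and 24.6% in the three rows, with no difference in risk.

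**5. Opposite direction.** Use the week-3 response of 27/32 and 1/8 from Protocol 3.2.4.3. Responders start cycle 1 at week 3 (8 weeks of IP), and non-responders leave IP after 4 weeks.
- Romiplostim: 0.844 × 8 + 0.156 × 4 + 4.3 = 11.7 weeks.
- Placebo: 0.125 × 8 + 0.875 × 4 + 4.3 = 8.8 weeks.

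An event with 20% incidence over a responder's 12.3-week window would then show as 19.1% on romiplostim and 14.7% on placebo, again with equal risk.

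**The case against.** **Much of the safety analysis is already time-aware.** Events of interest get duration-adjusted rates. Grade ≥ 2 bleeding has an Andersen-Gill model, survival has log-rank and Cox analyses, and MDS and secondary malignancy have Kaplan-Meier curves and hazard ratios. IP exposure is summarized by arm, and adverse event listings extend beyond the TEAE window. The general tables are descriptive, without formal testing. This stands, and it limits the point to those tables. The exposure summary can reveal an imbalance but does not adjust the percentages for it.

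**A reader might infer that the arms will be observed for systematically different times.** The documents do not establish that. The 12-week wait is discretionary, cycle 1 may start from week 4, persistent non-response at the maximum dose stops IP, and SAP 8.4 anticipates earlier placebo drop-out. A difference is plausible, but its size and sign are unknown.

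**A reader might also hold only placebo non-responders to week 6 or 8**, which would give 20% and 28% in place of 16% and 21%. In a double-blind trial an arm-specific waiting rule is not credible.

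**The inputs are soft.** The week-3 romiplostim figure is an interpolation. Protocol 10.1 also cites spontaneous recovery of 5 of 22 (23%), which would lower the shares to 10%, 15% and 18%. Primary-endpoint failures include reductions and omissions that cause no delay. In the base case the artefact at 20% incidence is about 2 points, against a standard error of √(0.2 × 0.8 × (1/108 + 1/54)) = 6.7 points. All of this stands, and it makes the figures illustrative.

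**Rates have their own weakness.** Extra waiting time before chemotherapy is lower-risk person-time, so dividing by it could dilute the placebo rate and make romiplostim look worse. Rates also do not cure informative stopping. This is why they should not replace the percentages.

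**Conclusion.** The point holds in limited form. The general TEAE categories in SAP 9.6.1 are crude percentages over a window that can range from 11.3 to 25.3 weeks and depends on a post-randomization response to treatment. Observation time may therefore differ by arm, in either direction.

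Under the stated assumptions, 10% to 21% of placebo observation time lies beyond the shorter window. For an event with 20% incidence that amounts to about 2 to 5 percentage points of artefact, and the sign reverses if placebo subjects leave IP early. These figures rest on small cited studies, a common waiting rule and a constant hazard.

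The documents do not support saying that all safety comparisons are non-comparable, nor that the bias runs in a known direction. What is missing is a means for the reader to judge the general tables.

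**What to change.** In SAP 9.6.1, for the overall TEAE categories already listed and not for every system organ class and preferred term:
- Keep the crude percentages.
- Beside them, add the exposure-adjusted incidence rate by arm: subjects with a first event per 100 subject-years at risk, from first IP to the earlier of last IP + 30 days or end of study. Time at risk ends at the first event.
- Report the mean and median length of the TEAE window by arm.
- Present the rates as a supplement and not as the sole basis for safety conclusions. State that they assume a roughly constant hazard and non-informative stopping.

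The cost is SAP wording and a few extra table columns, with no new data and no change to conduct. The downside is that the denominator includes lower-risk waiting time before chemotherapy, which should be said next to the rates.
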